Most individuals with inflammatory myelopathy have lost normal voluntary control of lower extremity function. Functional Electrical Stimulation cycling with the RT-300 allows the equivalent of 6000 step cycles in one hour (when cycling at 50 rpm), a little over half the normal number of steps a healthy adult takes on average per day. Six lower extremity muscle groups are simultaneously stimulated with this device. It is therefore the most efficient device in delivering electrical stimulation to subjects with complete spinal cord injury and was therefore chosen for this study.

The RT-300 FES bike has been FDA-cleared for use in general rehabilitation (the device clearance number is K072398). It has been a standard rehabilitation treatment modality at our center for several years.

7. Study Statistics

- a. Primary outcome variable.

BDNF CSF level testing

BDNF levels in the CSF of the study subjects will be measured in response to FES ergometry. BDNF has been linked to improved functional outcomes following CNS injury. We therefore chose BDNF as a surrogate marker to determine FES efficacy.

- b. Secondary outcome variables.

CSF analysis

Exploratory analysis to further understand the CSF response to FES cycle ergometry. It will be aimed at examining neurotrophins and define the molecular signature of repair in the CSF of patients with spinal cord injury.

Spasticity level:

Date: May 10, 2016
Principal Investigator: [name].
Application Number: NA_00041441

FES cycle ergometer therapy is expected to improve spasticity. This will be assessed by Modified Ashworth testing.

- c. Statistical plan including sample size justification and interim data analysis.

Sample size and power:

This is a dose finding clinical trial. Because there is limited data on BDNF CSF levels, the sample size cannot be computed at this time (power analysis cannot be performed). Instead we will use an adaptive sample size re-estimation strategy. Based on *in vivo* BDNF animal data we decided an effect size of 20% to be significant⁸⁰.

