After enrolling 48 subjects (12 per group) we will estimate 2 quantities: the mean BDNF CSF level per group and the within group standard deviation of BDNF levels (averaged across the 4 groups). The sample size may then be adjusted based on the estimated effect size (estimated mean per treatment group - 80% of that estimated mean) and the estimated standard deviation. If the recalculated total sample size is equal or less than 100 then the study will proceed. Otherwise the study will be terminated at that point.

The required sample size will be computed such that it provides 80% probability of correctly selecting the amount of FES that yields the highest mean BDNF given a true 20% mean difference between the highest mean and the next highest mean.

Analysis plan:

Dependent Variables: CSF BDNF concentration, Serum BDNF concentration, CSF GDNF concentration, CSF NT-3 concentration, CSF NT-4 concentration, CSF CNTF concentration, CSF NGF concentration, CSF IL-6 concentration, CSF IL17 concentration, CSF TNF α concentration, CSF IL-1 β concentration, CSF IL-23 concentration, CSF IL-12 concentration, modified Ashworth score, mood.

Independent Variables: Intervention (FES ergometry); Timing

Approach: The distributions of all outcome variables (CSF BDNF concentration, Serum BDNF concentration, CSF GDNF concentration, CSF NT-3 concentration, CSF NT-4 concentration, CSF CNTF concentration, CSF NGF concentration, CSF IL-6 concentration, CSF IL17 concentration, CSF TNF α concentration, CSF IL-1 β concentration, CSF IL-23 concentration, CSF IL-12 concentration, modified Ashworth score, mood) will be described by treatment group (mean, median, standard deviation). The group that has the highest mean change in BDNF concentration will be used for further studies (future Phase 3 clinical trial).

Exploratory analysis will be performed to compare mean values of GDNF, NT-3, NT-4, CNTF, NGF, IL-6, IL17, TNF α , IL-1 β , IL-23, IL-12 concentration among the 4 groups using analysis of variance or suitable non-parametric methods (Kruskal-Wallis Test) if the outcome appears to be non-normally distributed.

- d. Early stopping rules.

The principal investigator may discontinue the study if the interim statistical analysis as described above indicates that the number of subjects required for this trial exceeds #80.

Patients may withdraw from the study at any time for any reason. Any investigator may discontinue a patient for any of the following reasons:

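### The sample size and the go/stop decision are computed from BDNF levels but the regimen is selected on mean change, so the 80% probability of correct selection is not calibrated for the rule used

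*Combined protocol and SAP*

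**What the plan says.** Section 7.c (Sample size and power) gives no initial N: "Because there is limited data on BDNF CSF levels, the sample size cannot be computed at this time". It relies on a re-estimation instead: "After enrolling 48 subjects (12 per group) we will estimate 2 quantities", namely "the mean BDNF CSF level per group and the within group standard deviation of BDNF levels (averaged across the 4 groups". The effect is on the same scale: "estimated effect size (estimated mean per treatment group - 80% of that estimated mean". N is chosen to give "80% probability of correctly selecting the amount of FES that yields the highest mean BDNF". The configuration assumed for that probability is then stated as "given a true 20% mean difference between the highest mean and the next highest mean". The result also decides whether the trial continues: "If the recalculated total sample size is equal or less than 100 then the study will proceed"; otherwise it is terminated. Section 7.d lets the principal investigator stop the study at a different limit, a required number above 80.

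The Analysis plan in 7.c uses another statistic: "The group that has the highest mean change in BDNF concentration will be used for further studies (future Phase 3 clinical trial". This agrees with the primary objective in section 2, which is about the increase in CSF BDNF. Section 4 (Study Design) has CSF BDNF measured at baseline and again after 3 weeks. Section 7.c does not say which visit supplies the levels used at the interim.

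**The concern.** The 80% is the only operating characteristic in the plan, so it should describe the rule that picks the regimen. The spread of a change score depends on the SDs at both visits and on their correlation (rho). The documents give neither rho nor the SD of change, and neither is among the two interim quantities.

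If rho is low, the trial can proceed with too few subjects for its own selection rule. If rho is high, it can be terminated although that rule needed fewer. Either error would come after 48 people had entered a study with two lumbar punctures each, and the selected regimen goes forward to Phase 3.

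**Working it through.** **Inputs.** From 7.c: four groups, 12 per group at the interim, a gap of 20% of the mean, an 80% target, and termination above 100. The correlation rho and the coefficient of variation of levels (CV = SD/mean) are not in the documents. All values used for them are assumptions.

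**The plan's own target.** For k arms with normal means and a common SD, and the others tied one gap below the best, the probability of correct selection is the integral of φ(z)·Φ(z+t)^(k−1) dz, with t = gap·√n/SD. Setting this to 80% gives t = 1.893 for k = 4 and 1.652 for k = 3. Sizing on levels then needs n per group = (t·CV/0.20)². No N can be reproduced because no SD is given. The target is attainable on levels: with four arms, N ≤ 100 needs CV ≤ 0.20·√25/1.893 = 0.528.

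**Same N, selection on change.** With equal visit SDs, SD(change) = SD(level)·√(2(1−rho)), so t becomes t/√(2(1−rho)):

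| rho | four arms | three arms |
|---|---|---|
| 0 | 66% | 68% |
| 0.3 | 73% | 74% |
| 0.5 | 80% | 80% |
| 0.7 | 90% | 89% |
| 0.8 | 96% | 94% |

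If the Week 3 SD is 1.25 times the baseline SD, the crossing point moves from rho 0.5 to 1/(2×1.25) = 0.40 if the interim uses the Week 3 SD, or to 1.25/2 = 0.625 if it uses the baseline SD. The unstated visit therefore matters.

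**Go/stop (four arms).** N on change is 2(1−rho) times N on levels, before rounding.
- CV 0.45: (1.893×0.45/0.20)² = 18.14, so 19×4 = 76 on levels. At rho 0.3, 18.14×1.4 = 25.4, so 26×4 = 104 on change. Levels say proceed; change says terminate.
- CV 0.60: 32.26, so 33×4 = 132 on levels. At rho 0.7, 32.26×0.6 = 19.4, so 20×4 = 80 on change. Levels say terminate; change says proceed.

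**When the 48 already suffice.** With 12 per group, selection on change reaches 80% if CV ≤ 0.20·√12/(1.893·√(2(1−rho))). This is 0.26 at rho 0 and 0.31 at rho 0.3 (four arms). The spreads in section 3 give 1.07/6.16 = 0.17 and 37/242 = 0.15 if they are SDs. Correct selection on change with 48 subjects is then 94% and 97% even at rho 0.

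**Whole rule simulated** (four arms, normal data, Week 3 means 1, 0.8, 0.8, 0.8, gap 20% of the highest estimated mean, at least 12 per group, stop above 100). Each cell gives the percentage of trials that proceed, then the percentage of those that select correctly:

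| Assumed values | sized on levels, selected on change | sized and selected on change | sized and selected on baseline-adjusted mean |
|---|---|---|---|
| CV 0.45, rho 0.3 | 91 / 74 | 57 / 80 | 95 / 81 |
| CV 0.60, rho 0.7 | 34 / 85 | 88 / 78 | 95 / 79 |

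Two further choices move these rates as much as the SD does. At CV 0.45 and rho 0.3, a stop above 80 instead of 100 lowers the three proceed rates to 71%, 28% and 81%. Taking the 20% from the pooled mean instead of the highest mean (stop at 100) lowers them to 51%, 12% and 65%.

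**The case against.** The strongest reply is that this is loose drafting. Section 7.a names the outcome as BDNF level testing in response to FES, so 'level' may be shorthand for the outcome. Under randomisation, the arm with the highest expected Week 3 level is also the arm with the highest expected change. That is correct, but N and go/stop depend on precision, and precision differs between the two statistics. The shorthand reading does not repair the text either. If 'level' means change, the 20% becomes 20% of a mean change, which is a different gap. If it means baseline, the interim means carry no treatment information.

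The second reply is that no harm is shown from the documents, and this largely stands. The CVs that produce harm are assumed, and the printed spreads are harmless if they are SDs. Section 3 does not say whether they are SDs or standard errors. If they are standard errors, an assumed 5 to 30 subjects gives CVs from 0.153×√5 = 0.34 to 0.174×√30 = 0.95. The same section reports widely varying concentrations, and the re-estimation exists because the spread is not known.

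The third reply is that tied arms are the least favourable case, while the protocol expects more sessions to do better. This also stands. If the arms step down by one gap each, correct selection on change at the level-based N is 82% at rho 0 and 87% at rho 0.3, against 91% on levels.

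A reader might infer that the trial is under-sized, or that the 80% is right only at rho 0.5. The documents support neither. Rho is unknown, so the error may run either way. The 0.5 crossing needs equal visit SDs, tied arms and an N set by the recalculation rather than by the 48 already enrolled.

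**Conclusion.** The mismatch is plain in the current text of 7.c. Sizing and go/stop use the mean and SD of levels at an unnamed visit, while selection uses mean change. The 80% is therefore uncalibrated for the rule that chooses the regimen.

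Its size is conditional. Over assumed correlations of 0 to 0.8, correct selection runs from 66% to 96%, given equal visit SDs, four arms with three tied 20% below the best, and N set by the recalculation. Go/stop can flip in both directions at the assumed CVs of 0.45 and 0.60. There is no harm if the level CV is at most about 0.26 with four arms at rho 0. Confidence is high in the textual mismatch and lower in its consequence, which depends on quantities that the documents do not give. It should be fixed before the interim.

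**What to change.** Use one statistic in 7.c for sizing and selection.
- **Preferred:** select on the Week 3 mean adjusted for baseline CSF BDNF (ANCOVA). At the interim, compute N and go/stop from the pooled residual SD of that model, in subjects with both CSF samples. This still addresses the increase in BDNF.
- **Minimum:** keep selection on mean change, and size on the pooled within-group SD of change in subjects with both samples.
- **In either case:** define the gap as an absolute difference equal to 20% of the highest arm's estimated mean Week 3 level, which fits the highest mean already named in 7.c. State whether three or four arms compete, because t and hence N differ. Reconcile the N limit of 100 in 7.c with that of 80 in 7.d, because the proceed rates depend on it.

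Costs: wording and one further interim estimate, with no new samples. The interim may wait about 3 weeks for the last Week 3 samples. With the minimum fix and a low correlation the trial stops more often: at CV 0.45 and rho 0.3 it proceeds in about 57% of trials rather than 91%. Estimating the ANCOVA slope costs about 0.5 percentage points of correct selection near rho 0. Because N is estimated from 48 subjects and capped, realised correct selection can still fall slightly below 80% under either fix, at about 78% to 79% for CV 0.60 and rho 0.7.

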The discrepancies of the different BDNF levels might be explained by the difference of assays used. BDNF assays are now commercially available (RayBiotech, Norcross GA, USA). With this assay the minimum detectable dose of BDNF is typically less than 0.3 ng/ml without cross reactivity to other cytokines (Reproducibility - Intra-Assay: CV<10%, Inter-Assay: CV<12%).

4. Study Procedures

Study Design:

Phase 2 trial.

This selection study will be performed as a randomized, parallel Group Trial to determine the amount of FES ergometry required to achieve maximal CSF BDNF levels in individuals with inflammatory myelopathy.

Subjects will be randomized into 4 groups (FES1: 1 session of FES ergometry per week, FES3:3 sessions of FES ergometry per week, FES5: 5 sessions of FES ergometry per week, and Passive: 3 sessions of passive cycling per week). Session duration is 60 minutes. After obtaining a detailed physical and spasticity testing, baseline serum and CSF BDNF levels will be measured. The subjects will then receive

FES ergometry or passive cycling according to their group assignment for 3 weeks. At that time the subjects will return for a physical exam, spasticity testing, and repeat serum and CSF BDNF level testing. The primary investigator will be blinded to the results. The Study Time Line is found in Figure 1.

[figure not shown]

Figure 1: Study Time Line

Study Treatments

All activities will be conducted at INI and are supervised by a licensed physical therapist. This includes all cycling activities; all study procedures, the screening and final visits. Urine (for rapid urine pregnancy testing) will be sent to the Johns Hopkins Medicine (JHM) Pathology lab.

Functional Electrical Stimulation Ergometry

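### Read as written, the interim re-estimation averages the four group SDs, which gives a slightly smaller sample size and a slightly easier go decision than the pooled within-group SD

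*Combined protocol and SAP*

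**What the plan says.** Section 7.c (Sample size and power) gives no planning SD and no initial sample size, and relies on an interim re-estimation: "After enrolling 48 subjects (12 per group) we will estimate 2 quantities". These are the mean CSF BDNF level in each group and "the within group standard deviation of BDNF levels (averaged across the 4 groups"). The effect size is 20% of a group mean, written as "estimated mean per treatment group - 80% of that estimated mean".

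The new sample size is chosen so that "it provides 80% probability of correctly selecting the amount of FES that yields the highest mean BDNF". The gap between arms assumed for this purpose is one fifth, separating the best arm from the runner-up. The result also decides whether the trial continues: "If the recalculated total sample size is equal or less than 100 then the study will proceed"; otherwise it stops. Section 7.d gives a different limit: the principal investigator may stop if the interim analysis "indicates that the number of subjects required for this trial exceeds #80".

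No formula for the averaging is given. Neither the variance nor a pooled estimate is mentioned.

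**The concern.** The SD is the only measure of variability in the trial's only sample size calculation, and no planning value stands behind it. It sets the final N and helps decide whether the trial proceeds. The required N is proportional to the square of the SD, so the natural estimate is the average of the group variances, which is unbiased for the true mean within-group variance.

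Averaging SDs and then squaring gives a smaller number unless all four observed SDs are identical. The departure always has the same sign: towards fewer subjects and towards proceeding. What needs settling is its size.

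**Working it through.** **Inputs from the protocol.** Four arms (section 4, Study Design: "Subjects will be randomized into 4 groups"); 12 per arm at the interim; 80% probability of correct selection; a 20% gap between the best and second-best mean; proceed if N is at most 100. The plan states no recalculated N and no SD, so there is no figure of its own to reproduce beyond 4 × 12 = 48.

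**Assumptions.** The documents give no coefficient of variation (CV = SD/mean) for this population, so a range is used. The 20% difference is treated as known, so that only the SD estimator varies. The other three means are taken as equal to each other (the standard selection set-up).

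**Step 1: sample size formula.** For selecting the best of four arms, n per arm = (h × SD/δ)², where h solves ∫Φ(x + h)³φ(x)dx = 0.80. This gives h = 1.893. With δ = 0.20 × mean:

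N = 4 × (1.893 × CV/0.20)², rounded up per arm.

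- CV 0.40: N = 57.3 before rounding
- CV 0.50: N = 89.6
- CV 0.53: N = 100.7
- CV 0.60: N = 129.0

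**Step 2: direction.** With equal group sizes, (mean of s₁…s₄)² = mean of s² minus the variance of the four s values (divisor 4). The averaged SD therefore never exceeds the pooled SD, whatever the data.

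**Step 3: size with normal data and equal SDs.** For n = 12, E(s) = c₄σ with c₄ = 0.97756, so c₄² = 0.9556. Then

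E[(mean of four s)²]/σ² = c₄² + (1 − c₄²)/4 = 0.9556 + 0.0111 = 0.967.

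The pooled variance has ratio 1. N is thus 3.3% low on average: 100.7 × 0.967 = 97.3 at CV 0.53. Replacing h by 1.893 × √0.967 in the integral gives a correct-selection probability of 0.793 instead of 0.800.

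**Step 4: the go decision.** 50,000 simulated interim data sets, 4 × 12, normal, equal SDs:

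| CV | Median N, averaged | Median N, pooled | P(N ≤ 100), averaged | P(N ≤ 100), pooled |
|---|---|---|---|---|
| 0.40 | 56 | 60 | 0.999 | 0.998 |
| 0.50 | 88 | 92 | 0.774 | 0.721 |
| 0.53 | 96 | 100 | 0.581 | 0.517 |
| 0.60 | 124 | 128 | 0.178 | 0.141 |

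**Step 5: unequal SDs or skew (assumed cases).** Suppose one arm has double the SD of the others. The mean SD is (1 + 1 + 1 + 2)/4 = 1.25 and the mean variance is (1 + 1 + 1 + 4)/4 = 1.75. Then

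(0.9556 × 1.25² + 0.0444 × 7/16)/1.75 = (1.493 + 0.019)/1.75 = 0.864.

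N is about 14% low. With a base CV of 0.40 the true N is 57.3 × 1.75 = 100.4. The simulation gives a median N of 88 averaged and 100 pooled, and P(N ≤ 100) of 0.763 and 0.544. Correct selection at the reduced N is about 0.77, by an equal-variance approximation.

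Milder and skewed cases, as the ratio of expected N to the N implied by the true mean variance:

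- one arm at 1.5 times the SD, normal: 0.933
- lognormal, CV 0.50: about 0.92
- lognormal, CV 0.75: about 0.87

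Pooling gives about 1.00 in every case.

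**Step 6: small CV.** Section 3 quotes CSF BDNF values of 6.16 ± 1.07 and 242 ± 37 pg/ml. It does not say whether the ± is an SD. If it is, the CVs are 1.07/6.16 = 0.174 and 37/242 = 0.153. The formula then gives 2.7 and 2.1 per arm, so N = 12 in both cases, well below the 48 already enrolled. The choice of estimator then has no effect.

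**The case against.** **The wording is ambiguous.** The text names one within-group SD and adds a parenthesis. With 12 per group, the pooled SD is the root of the variances averaged over the four groups, so the phrase could be shorthand for it. This stands. A reader might infer that the plan considered pooling and rejected it; nothing in the documents shows that. Averaging SDs is the literal reading, not an established intention.

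**The base-case effect is small.** This also stands: one subject per arm and under one percentage point of correct selection. The larger figures rest on assumed distributions.

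**Averaging does not explain a failure to reach 80%.** A reader might infer that it does. Simulating the whole procedure (60,000 runs, no dropout) gives correct selection of 79.6% averaged and 79.9% pooled for normal data at CV 0.50. For lognormal data with CV 0.60 and means 1, 0.8, 0.8, 0.8, it gives 76.4% and 78.0%. Pooling recovers under two points there and still misses 80%; most of the shortfall has other causes, such as estimating a variance from 48 subjects.

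**A higher chance of proceeding is not always an error.** In that lognormal case P(N ≤ 100) is 0.75 averaged and 0.66 pooled. But the true N is 4 × (1.893/0.20)² × 0.36 × (1 + 3 × 0.64)/4 = 94.2, under the limit of 100, so proceeding is the right decision there under 7.c. The example does not show wrong decisions.

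**Other gaps in the same rule matter as much or more.** The limits of 100 (7.c) and 80 (7.d) conflict and must be reconciled. The re-estimation uses BDNF levels while selection uses mean change. The group mean that defines the 20% is not specified. These are separate points. They lower the priority of this one but do not remove it, because the direction in step 2 holds under either limit.

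**Conclusion.** The point holds on the literal reading of 7.c, as a minor defect with a one-directional effect. That the averaged SD never exceeds the pooled SD is certain. How much this matters depends on quantities that the documents do not give.

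- Normal data, equal SDs: N about 3.3% low. The chance of proceeding rises by about 4 to 6 points for CVs from 0.50 to 0.60 (0.58 against 0.52 at a true N of about 101), and by about 0.1 point at CV 0.40.
- Unequal SDs or skew: N is 8 to 14% low in the assumed lognormal and doubled-SD cases. With one arm at double SD and a true N of about 100, the chance of proceeding is 0.76 against 0.54. Only here is the effect material.
- CV near 0.16: none.

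If a pooled SD was meant, nothing is biased, but the text still leaves the key input unspecified.

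**What to change.** In section 7.c, replace the phrase on the averaged SD with: *the pooled within-group SD (square root of the mean of the four group variances, i.e. of the residual mean square from the four-group model; 44 df with 12 per group)*.

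This costs a few words and no extra data. The downside is that the recalculated N is slightly larger on average and the trial proceeds slightly less often. That includes some cases where the true N is under the limit: at CV 0.50 with normal data (true N 89.6), the chance of proceeding falls from 0.774 to 0.721.

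A move to the log scale should not be attached to this edit. The plan selects on the arithmetic mean change in BDNF, which can be negative, so a log-scale analysis would change what is being compared.

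### Sections 7c and 7d set different limits for the same 48-subject interim: at a re-estimated total of 81 to 100, one orders the trial to continue and the other lets the investigator stop it

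*Combined protocol and SAP*

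**What the plan says.** Section 7c of the protocol (statistical plan, sample size and interim analysis) explains that, because CSF BDNF data are limited, "the sample size cannot be computed at this time (power analysis cannot be performed"). It continues: "Instead we will use an adaptive sample size re-estimation strategy".

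The interim is defined in the same section: "After enrolling 48 subjects (12 per group) we will estimate 2 quantities", namely the group means and the average within-group standard deviation. The total is then recalculated so that "it provides 80% probability of correctly selecting the amount of FES that yields the highest mean BDNF", given a true 20% gap between the best and second-best means. The decision rule is two-way and mandatory: "If the recalculated total sample size is equal or less than 100 then the study will proceed". For any larger total: "Otherwise the study will be terminated at that point".

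Section 7d (early stopping rules) gives a second rule for that interim, as a permission tied back to 7c: "The principal investigator may discontinue the study if the interim statistical analysis as described above". The condition attached to this permission is a required total above 80; in the protocol's words, that the analysis "indicates that the number of subjects required for this trial exceeds #80".

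**The concern.** Both rules act on one quantity, the total number of subjects required, at one time point, the 48-subject interim. Section 7d's back-reference can only mean the re-estimation in 7c, because no other interim analysis is described. Yet the limits are 100 and 80, and the force differs: 7c is an instruction, 7d a permission.

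In many trials such a slip would be minor, because a fixed target would stand behind it. Here there is none. The re-estimation takes the place of a sample-size calculation, so this rule settles whether the trial continues and how large it may become. At 81 to 100, one reader could follow 7c and continue while another relied on 7d and stopped, each citing the protocol. The choice would also be made after BDNF means by group have been estimated, which is when an unspecified discretion is least desirable.

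**Working it through.** **1. The plan's own figures.** 12 per group in 4 groups gives 4 × 12 = 48, as stated. The limits 80 and 100 are decision thresholds, not computed sample sizes, and no standard deviation is given, so there is nothing further to reproduce.

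**2. The two rules side by side, by recalculated total N.**

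| N | Section 7c | Section 7d | Result |
|---|---|---|---|
| 80 or less | continue | no ground to stop | agree |
| 81 to 100 | continue (mandatory) | investigator may stop, no criteria given | conflict |
| above 100 | terminate (mandatory) | investigator may stop | differ in force only; terminating satisfies both |

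**3. Totals affected.** Assuming equal groups, N is a multiple of 4. In the conflict range that means 21 to 25 per group: 84, 88, 92, 96 or 100.

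**4. Participants affected.** Assuming also a pause in enrolment at 48 (the text states none) and no withdrawals (the text allows them), the further enrolment at issue is 84 − 48 = 36 up to 100 − 48 = 52.

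**5. Can the range be reached?** Assume normal BDNF values, equal standard deviations and every other arm 20% below the best. The probability of correct selection among k arms is then ∫ φ(x) Φ(x + h)^(k−1) dx, with h = δ√n / SD. Setting this to 0.80 gives h = 1.893 for k = 4. With δ equal to 20% of the mean, n per group = (1.893 × CV / 0.20)², where CV is SD divided by mean. Then n = 20 (total 80) corresponds to CV = 0.20 × √20 / 1.893 = 0.472, and n = 25 (total 100) to CV = 0.20 × √25 / 1.893 = 0.528.

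The CV is not in the documents. A simulation of the interim estimate (12 per group, pooled SD on 44 degrees of freedom, δ taken as 20% of the largest sample mean) gives these chances that the re-estimated total lands in 81 to 100:

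| Assumed true CV | Chance of 81 to 100 |
|---|---|
| 0.40 | 7% |
| 0.45 | 20% |
| 0.50 | 27% |
| 0.55 | 26% |
| 0.60 | 21% |
| 0.70 | 9% |

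**6. What stopping at 48 would mean for the selection (illustrative).** If n per group is truly what the 80% target requires, then 12 per group gives h₁₂ = h × √(12/n), and no SD is needed. For the three FES arms alone (k = 3), h = 1.652.

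| Arms | n required | h₁₂ | Probability of correct selection at 12 per group |
|---|---|---|---|
| 4 | 21 | 1.893 × √(12/21) = 1.431 | 0.683 |
| 4 | 25 | 1.893 × √(12/25) = 1.312 | 0.648 |
| 3 | 21 | 1.652 × √(12/21) = 1.249 | 0.703 |
| 3 | 25 | 1.652 × √(12/25) = 1.145 | 0.675 |

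These figures matter only if a terminated trial would still select an arm, which the text does not say.

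**The case against.** The strongest reply is that both rules can be obeyed at once. Section 7d only permits stopping, so continuing at 81 to 100 breaches neither section. On that reading 7c is the default and 7d a discretionary exception: optional stopping above 80, mandatory stopping above 100. This may be what was intended. It is not what is written. The order to continue in 7c is unqualified and does not mention 7d, so using the permission in 7d would breach 7c. If two tiers were meant, the criteria for using the discretion are missing.

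A second reading is that 80 counts evaluable subjects and 100 counts enrolled ones, since 80 / (1 − 0.20) = 100. No dropout rate is stated, and 7d speaks of the number the trial requires, so the text does not support this.

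Two further points stand. The conflict arises only if the re-estimate falls in one window, which under the assumptions above is the less likely outcome at every CV tried. And the loss of selection probability in step 6 follows from any termination at 48, including the one 7c itself orders above 100, so it does not measure the cost of the mismatch as such. Neither point removes the contradiction. A chance of up to about one in four is not negligible, and step 6 is offered only as illustration.

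**Conclusion.** The concern holds, and the text must be corrected. The contradiction follows from the wording alone, at a recalculated total of 81 to 100. Above 100 there is a lesser mismatch between an order and a permission. The documents do not show which limit is right, and 7d sets no maximum enrolment; the only upper limit in the text is the 100 in 7c.

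The practical size, 36 to 52 further participants or none, rests on equal groups, a pause at 48 and no withdrawals. The chance of landing in the window rests on an assumed CV and on the normal, equal-variance, equal-gap model. The conclusion depends on none of these. The error rate of a test is not affected, since the best arm is to be chosen by its mean change in BDNF and not by a test.

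**What to change.** Amend 7c and 7d before the 48-subject interim, so that the limit is not chosen once the re-estimate is known. There are two acceptable forms:

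- one limit on the recalculated total, in the same wording and with the same force in both sections; or
- an explicit two-tier rule that says stopping is optional in the range 81 to 100 and mandatory above it, gives the criteria for using the discretion, and makes the order to continue in 7c subject to it.

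In either case, state the resulting maximum total. The sponsor must say which was intended. The cost is a wording amendment; it adds no participants or procedures in itself.
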